### **6.3.6 Vital Signs**

Vitals signs include systolic/diastolic blood pressure, heart rate, respiratory rate, temperature, and weight.

Baseline value is the subject's last observation prior to the initiation of study drug (including Cycle 1 Day 1).

### **6.3.7 Electrocardiogram (ECG)**

The electrocardiogram assessment includes the QT Interval (msec), QTc Interval (msec), RR Interval (msec) and the general result (interpretation).

### **6.3.8 Physical Examination**

A physical examination will be performed at baseline and at each cycle, but no result from the physical examination will be entered in the database. The significant findings from the physical examination will be reported in the Medical History (prior to study drug administration) or the Adverse Event (after study drug administration) forms.

### **6.3.9 Pregnancy Test**

A pregnancy test will be performed at baseline and at the End of Treatment and 30-day Safety Follow-up visit for females with childbearing potential.

### **6.3.10 Concomitant Medications and Therapies**

Concomitant medications will be collected for all visits.

Verbatim descriptions of concomitant medications and therapies will be mapped to the World Health Organization (WHO) Drug Dictionary Enhanced (WHO-DDE) and Herbal Dictionary (WHO-HD) (version Q1 2016).

**Concomitant medication/treatment** is any medication/treatment with start date on or after the initial dosing of TAS-114 or S-1, whichever occurs first. Medication/treatment that started before the first dose and continued during the study treatment will also be counted as concomitant medication/treatment.

#### Concomitant Medications Counting Rules:

A patient with more than one different medications in a particular medication class will be counted only once in the total of patients taking that particular medication class.

A patient having the same medication more than once during the study will be counted only once in the number of patients with that medication.

Medications with Incomplete Dates:

For concomitant medications with missing or partially missing start dates, they will be imputed, if necessary, using the same algorithm described for adverse event onset dates (see Section 6.3.3). If the stop date is missing or partially missing, the imputation rule is applied in the following order:

- 1) *year is missing* - the medication will be considered to have been received at all periods after that period determined by the start date. Date left missing.
- 2) *month is missing* - impute 'December'.
- 3) *day is missing* - impute 'last day of that month'.

**6.3.11 Other Diagnostics and Procedures**

Other diagnostics and procedures are collected though the entire study.

**6.3.12 New Anti-Cancer Treatments**

New anti-cancer treatments are collected after the patients discontinue the study treatment on the Post-Treatment form.

Medications with Incomplete Dates:

When checking to see if anti-cancer treatments is initiated prior to a response assessment in cases where the start date of the anti-cancer therapy is only partially provided, use the last day of the month if the day is missing. If the month or year is missing do not impute a date and do not count the patient as having received anti-tumor therapy.

**7. STATISTICAL ANALYSIS**

**7.1 General Data Handling Rules and Definitions**

All data collected on case report forms will be provided in listings, except data collected only for confirmation of study entry criteria and for study administrative purposes. If any randomized patient is found to not have valid documented informed consent, that patient's data will be excluded from the report, except as necessary to document the error.

All analyses will be conducted using SAS version 9.4.

Except where specified, all continuous variables will be summarized with descriptive statistics (number of non-missing values, mean, standard deviation, median, Q1 and Q3, minimum and maximum) and all categorical variables will be summarized with frequency counts and percentages, by treatment group.

Missing data will be maintained as missing unless specified otherwise. For variables where missing data is imputed, the analysis dataset (ie. ADaM) will contain one variable with the imputed value and the original variable with missing maintained as missing.

## 7.2 Patient Disposition

The number of patients in each study population and the reasons for exclusion will be summarized. In addition, patients' status with regard to study treatment and follow-up will also be summarized, along with the reasons for study treatment discontinuation. The number of patients in each study population and reason for study treatment discontinuation will also be summarized by geographical region.

## 7.3 Protocol Deviations

A CSR reportable Protocol Deviation is related to inclusion/exclusion criteria, conduct of the trial, patient management or patient assessments that impact the safety of the subjects or jeopardize the quality of the study data.

During the conduct of protocol TAS-114-201 the following categories will be used for CSR reportable Protocol Deviations:

- A subject that did not meet entry criteria
- A subject that developed withdrawal criteria but was not withdrawn
- A subject that received the wrong treatment or incorrect dose
- A subject that received an excluded medication
- Critical ICF, GCP and other Protocol Deviations

A CSR non-reportable Protocol Deviation may be important to address and document as part of site management and oversight, but is not considered reportable in the CSR.

The following categories will be used to capture non-reportable PDs.

- SAE reporting
- Informed consent
- Study procedures
- Investigational product (other than incorrect dose or wrong treatment)

Refer to *Protocol Deviation Plan*, Section 2 for details.

The key protocol violations include, but are not limited to:

- No measurable disease (assessed by investigator or central independent review)
- Did not receive at least 2 prior therapies for advanced or metastatic disease condition, including platinum doublet and pemetrexed, docetaxel, or immunotherapy
- No documentation of histologically diagnosed or cytologically proven advanced or metastatic NSCLC patients, either Stage IIIB/Stage IV disease (according to Version 7 of the International Association for the Study of Lung Cancer Staging Manual in Thoracic Oncology), or recurrent disease following radiation therapy or surgical resection

The number of patients with deviations of one or more criteria and the number of patients with key protocol violations will be listed and tabulated for all patients (including screen failures) and ITT population.

#### **7.4 Demographic and Baseline Characteristics**

Demographics variables, baseline characteristics, cancer history, medical history/active symptoms and prior cancer treatment will be summarized by treatment group for the ITT population. Cancer history, prior systemic drug therapies, and standard prior systemic therapies (platinum doublet and pemetrexed, docetaxel, immunotherapy) will also be summarized by geographical region.

All the data fields will also be presented in patient data listings.

#### **7.5 Efficacy Analyses**

The following sections outline the planned analyses of the primary and secondary objectives of the study TO-TAS-114-201.

Comparison of time-to-event endpoints (PFS, OR and DR) will be based on the Cox proportional hazard model, stratified or unstratified, as specified, where the hazard ratio (HR), corresponding 90% and 95% confidence interval, and p-values will be estimated. Details of the hypothesis testing for the PFS analysis are described in [Section 3.3](#). Survival curves and the estimated median time-to-event will be provided by the Kaplan-Meier method (Kaplan and Meier, 1958).

Overall response rate (ORR) and disease control rate (DCR) will also be compared between treatment groups using Fisher's exact test.

Refer to [Appendix 2](#) for the SAS code used for the efficacy analyses.

##### **7.5.1 Primary Efficacy**

The progression-free survival analysis will be based on the ITT population.

PFS in the efficacy population will be compared between the TAS-114/S-1 and S-1 control treatment groups using the stratified log-rank test with a one-sided significance level of 5%. CCI

CCI

Median time to PFS for each group being compared will be estimated using the Kaplan-Meier method, along with the corresponding 95% CI. Confidence intervals for median progression-free survival will be based upon the methods of Brookmeyer and Crowley. The 25th and 75th percentiles will also be calculated. Kaplan Meier estimates of progression-free at 2, 4, 6 and 8 months and their confidence intervals (calculated with the log-log transformation methodology of Kalbfleisch and Prentice) will be tabulated. The Kaplan-Meier plots will be displayed.

## Statistical Analysis Plan

Protocol No. TO-TAS-114-201

Last Revision Date: 29NOV2017

The primary analysis for PFS will be conducted after 60 events have been observed based on independent assessment or after all patients have been followed for at least 3 months, whichever is later.

CCI

CCI

CCI

CCI

CCI

## 7.5.2 Secondary Efficacy

### 7.5.2.1 Overall Survival

The overall survival (OS) analysis will be based on the ITT population.

The estimate of the hazard ratio and corresponding 95% CI will be provided using a univariate CPH model (only treatment effect in the model). Median time to OS for each group being compared will be estimated using the Kaplan-Meier method, along with the corresponding 95% CI. Confidence intervals for the median will be based upon the methods of Brookmeyer and Crowley. The 25th and 75th percentiles will also be calculated. Kaplan Meier estimates at 3, 6, 9 and 12 months and their confidence intervals (calculated with the log-log transformation methodology of Kalbfleisch and Prentice) will be tabulated. The survival curves will be estimated using the Kaplan-Meier method. The unstratified log-rank test will be done for the comparison of treatment effect.

The stratified log-rank test will also be performed for the comparison of treatment effect using the same stratification factors used for PFS.

The same multivariable analysis as for PFS will be performed for OS.

OS will also be presented by geographical region.

### 7.5.2.2 Overall Response Rate and Disease Control Rate

The overall response rate and disease control rate analyses will be based on the Tumor Response (TR) evaluable population.

ORR and DCR in the efficacy population will be compared between the 2 treatment groups using Fisher's exact test. The estimates and differences will be presented along with the associated exact 95% CIs for each treatment group.

Best response will be summarized into four RECIST categories: complete response (CR), partial response (PR), stable disease (SD), and progressive disease (PD). The summary will also include a category for unevaluable patients if applicable.

CCI

ORR and DCR will also be presented by geographical region.

### **7.5.2.3 Duration of Response**

The duration of response analysis will be based on the TR evaluable population, only for patients that have a CR or PR response. Duration of response will be analyzed in the same manner as OS.

CCI

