6.3. S-1

In an S-1 Phase 2 study for 2nd line NSCLC, a total of 57 patients with advanced NSCLC received S-1 30 mg/m² of S-1 every 12 hours for 14 days followed by a 7-day recovery period repeated every 3 weeks until death, progression of disease, occurrence of intolerable side effects, withdrawal of consent, or removal by Investigator. The following conclusions can be drawn:

- Although the study did not meet the criteria for progressing to Stage 3, S-1 showed antitumor activity in NSCLC, achieving a best overall confirmed response rate of 7.1%.
- Median progression-free survival (PFS) (2.9 months) and OS were comparable to those observed with pemetrexed and docetaxel when used as 2nd-line treatment for patients with NSCLC.

- S-1 30 mg/m², administered orally BID from Days 1 through 14, with a recovery period on Days 15 through 21, demonstrated a safety profile consistent with previous reports of S-1.¹⁶

S-1 is approved in Japan for the treatment of NSCLC. However, whilst S-1 is approved in the European Union and a number of other Asian countries for the treatment of a number of other advanced cancers, it is not approved for the treatment of NSCLC elsewhere in the world. In addition, S-1 is not approved in the United States (US). As of January 24, 2016, over 1.7 million patients have been treated with S-1 in the post-authorization setting since first approval in 1999.

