### 6.2.2.3 Duration of Response

Duration of response is derived for those patients with objective evidence of PR or CR. DR (in months) is defined as the time from the first documentation of response (CR or PR) to the first documentation of objective tumor progression or death due to any cause: (date of first progression or death – date of first CR or PR +1)/30.4375.

Patients who are alive and progression free as of the analysis cut-off date will be censored at their last evaluable tumor response assessment before initiation of any new anti-cancer cancer treatment. Refer to **Table 4** for censoring rules for duration of response.

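### Duration of response is to be compared between arms by hazard ratio and log-rank test in responders only, a comparison that randomisation does not protect and that conflicts with the synopsis

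*SAP*

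**What the plan says.** SAP 7.5.2.3 sets the analysis set: "The duration of response analysis will be based on the TR evaluable population, only for patients that have a CR or PR response". It then gives the method by reference: "Duration of response will be analyzed in the same manner as OS". Protocol 14.1.2.2.3 carries the same instruction.

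The OS method is in SAP 7.5.2.1. "The estimate of the hazard ratio and corresponding 95% CI will be provided using a univariate CPH model (only treatment effect in the model"), and "The unstratified log-rank test will be done for the comparison of treatment effect". The section adds a stratified log-rank test, Kaplan-Meier rates at fixed times, and the multivariable analysis used for PFS (that model is not legible in the public copy).

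SAP 7.5 names DR separately: "Comparison of time-to-event endpoints (PFS, OR and DR) will be based on the Cox proportional hazard model", with hazard ratio, 90% and 95% intervals and p-values. (OR in that list is presumably a slip for OS.)

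SAP 6.2.2.3 starts the clock at response: DR "is defined as the time from the first documentation of response (CR or PR) to the first documentation of objective tumor progression or death".

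The Statistical Methods paragraph of the protocol synopsis says instead that efficacy data, DR among them, are to be summarised descriptively. The secondary objective is to investigate DR; only the PFS objective is to compare. No hypothesis, alpha or sample size is stated for DR.

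**The concern.** OS is analysed in everyone randomised, so its hazard ratio compares randomised groups. DR is analysed in a subset chosen by what happened after randomisation, and the choosing event, response, is itself a trial endpoint. Protocol 6.2 gives the rationale that TAS-114 can enhance the antitumour activity of 5-FU. If it does, the combination arm's responders include patients who would not have responded on S-1 alone, and the control arm's responders have no counterpart to them. The two groups then differ by construction, and adjustment for baseline covariates does not bring the randomisation back.

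What is at stake is the reading of a secondary endpoint. The report would carry a hazard ratio and p-value labelled as a treatment comparison on DR, with no causal meaning and little precision. If the added responders have short responses, their inclusion pulls the combination curve down even though no patient is worse off.

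**Working it through.** **The plan's own figure.** The only sizing is for PFS. With hazard ratio 0.524, one-sided 0.05, 80% power and 1:1 allocation, 4 × (1.645 + 0.842)² / (ln 0.524)² = 59.2, so 60 events, as stated. There is no corresponding figure for DR.

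**Expected control responders.** Planned sample size 124 at 1:1 gives 62 per arm. The only legible S-1 response rate is in Protocol 6.3, where "a total of 57 patients with advanced NSCLC received S-1 30 mg/m²", "achieving a best overall confirmed response rate of 7.1" percent. Then 62 × 0.071 = 4.4. The binomial 95% range for 62 patients is 1 to 9, with a 17% chance of 2 or fewer. Carrying that second-line rate into a trial that requires at least 2 prior therapies is an assumption.

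**Precision.** Assume 9 to 12 experimental responders (9/62 = 15% to 12/62 = 19%; the documents give no legible rate), and count every responder as an event, which is the best case. SE(log HR) = √(1/d₀ + 1/d₁); the 95% interval factor is exp(1.96 × SE); power for a halved hazard is Φ(ln 2 / SE − z).

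| Events, control v experimental | SE | 95% CI factor | Power, two-sided 0.05 | Power, one-sided 0.05 |
|---|---|---|---|---|
| 4 v 9 | √(1/4 + 1/9) = 0.601 | 3.2 | 21% | 31% |
| 4 v 12 | √(1/4 + 1/12) = 0.577 | 3.1 | 22% | 33% |

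**Direction.** Illustrative assumptions, none from the documents: exponential durations without censoring; control responders (7.1%) with mean DR 8 months; the same 7.1% on the combination improved to a mean of 10 months; a further 10% who respond only on the combination, with mean m. Every patient does at least as well on the combination.

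The large-sample Cox hazard ratio exp(β) solves ∫[f₁ − (f₀ + f₁) × S₁e^β / (S₀ + S₁e^β)] dt = 0. Here S₀ = 0.071e^(−t/8), S₁ = 0.071e^(−t/10) + 0.10e^(−t/m), and f = −dS/dt. The percentages come from 20,000 simulated trials of 62 per arm with the log-rank test. Mean time in response per randomised patient is 0.071 × 8 = 0.57 months on S-1 and 0.071 × 10 + 0.10m on the combination.

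| m (months) | HR in responders | Trials pointing against TAS-114 | Nominally significant against (two-sided 0.05) | Mean months in response, all randomised |
|---|---|---|---|---|
| 3 | 1.33 | 69% | 7.5% | 0.57 v 1.01 |
| 4 | 1.22 | 61% | 5.5% | 0.57 v 1.11 |
| 5 | 1.13 | 56% | 3.9% | 0.57 v 1.21 |
| 6 | 1.04 | 50% | 2.5% | 0.57 v 1.31 |
| 8 | 0.91 | 40% | 1.5% | 0.57 v 1.51 |

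The last two hazard ratios vary a little with the method of calculation (1.04 to 1.06, and 0.91 to 0.96); the side of 1 does not change. The all-randomised measure has the correct direction in every row.

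**The case against.** DR is an unpowered secondary endpoint in a Phase 2 trial. Its objective is to investigate, the only stated hypothesis concerns PFS, and ORR is reported alongside and would show any added responders. The synopsis already asks for descriptive reporting, so part of the remedy is reconciliation. All of this stands, and it limits the severity. It does not remove the comparison: SAP 7.5, SAP 7.5.2.3 and Protocol 14.1.2.2.3 prescribe it, with no caveat in the legible text. Nor can the synopsis be taken to override them, because the same sentence also lists PFS, which is plainly to be tested.

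A reader might infer that the analysis will show harm where there is benefit. The documents do not support that. They give no response durations and no legible experimental response rate, and the reversal needs added responders with clearly shorter responses. With so few responders an estimate above 1 arises about half the time with no difference at all, so 61% is only some 11 points above chance. Nominally significant harm at m = 4 occurs in about 5% of trials, against 2.5% by chance.

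A reader might also take four control responders as a feature of the trial. It is an extrapolation from a 57-patient second-line study.

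Finally, whether the multivariable analysis extends to DR is an inference from the reference to OS, and redacted text follows the DR paragraph. Neither point touches the hazard ratio, interval and p-value already prescribed in legible text.

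**Conclusion.** The concern holds in this form: the plan prescribes a between-arm hazard ratio, interval and log-rank p-value for DR in a set selected by a post-randomisation outcome, and this contradicts the synopsis. The lack of a causal reading follows from the design and needs no numerical assumption.

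The imprecision is conditional on the 7.1% rate carrying over, on 9 to 12 experimental responders and on every responder having an event. Given those, the interval factor is about 3.1 to 3.2 and power for a halved hazard is 21% to 22% two-sided (31% to 33% one-sided). Reversal is a possibility only. In the illustration the hazard ratio runs from about 1.3 down to between 0.91 and 0.96 as the added responders' mean goes from 3 to 8 months, with nominally significant harm in roughly 2% to 8% of trials.

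The primary PFS conclusion is unaffected, as are the OS and ORR analyses. The change should be made, but the trial does not depend on it.

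**What to change.** In SAP 7.5, remove DR from the list of compared time-to-event endpoints. In SAP 7.5.2.3 and Protocol 14.1.2.2.3, replace the reference to the OS method with by-arm descriptive reporting: number of responders, Kaplan-Meier median DR with 95% CI, and range. State that no hazard ratio or log-rank test will be produced for DR, nor any multivariable model that the reference to OS would carry over. This brings DR into line with the synopsis.

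Optionally, if a comparison is wanted, base it on all randomised patients. Either the probability of being in response over time or the mean time in response with non-responders at zero would serve. The mean needs a stated time horizon, and both need a rule for patients who start new anti-cancer treatment.

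The cost is a small wording change in both documents, fewer outputs, and the loss of the DR p-value. The protocol edit falls under the amendment procedure of Protocol 16.1 and can go with the next amendment. No new data, visits or patients are needed.

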### **7.5.2.4 Tumor Response Assessments - Investigator versus Central Independent Review**

The tumor response assessments based on the investigator's review will be compared to the tumor response assessments based on the central independent review (blinded radiological review):

- Discordance in best response will be tabulated
- Summary statistics for the number of days between investigator date of progression and central independent review date of progression will be displayed

CCI

## **7.1 Safety Analyses**

All safety data will be summarized by treatment groups in tables and presented in patient data listings. The analysis population for all safety analyses will be the as-treated population. Patients are assigned to treatment groups for safety analyses based on the study treatment they actually received.

### **7.1.1 Exposure of Study Treatment**

The TAS-114/S-1 or S-1 control administration profile will be summarized with mean, standard deviation, median, minimum, and maximum for the total dose received, number of treatment cycles received, and dose intensity. Dose reduction, dose modifications, dose interruptions, subsequent cycle delays, dose discontinuation of TAS-114/S-1 or S-1 control, and their corresponding reasons will also be tabulated by treatment group.

### **7.1.2 Duration of Follow-Up**

A summary table showing the duration of follow-up will be presented by treatment arm for the ITT population. The follow-up period is defined as the time starting on the date randomized until the last day of contact, or the day of withdrawal from study or the day of death, whichever occurs last. The duration of

follow-up will be analyzed using the reversed Kaplan-Meier method, where deaths will be censored on the date of death.

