- To investigate the safety and tolerability.

CCI

Study Design:

This is a randomized, open-label, Phase 2 study of TAS-114 administered in combination with S-1, to investigate the efficacy, safety and tolerability of the TAS-114/S-1 regimen in patients with advanced or metastatic NSCLC.

The study will be conducted internationally in 2 regions: Asian [Japan] and Western [Europe and US]. Patients will be randomized into TAS-114/S-1 arm versus S-1 control arm in a 1:1 ratio.

Randomization will take place once the consented patient has completed all the necessary baseline procedures and is deemed eligible for study entry. Treatment assignment will be done centrally using a dynamic allocation method (biased coin) via an interactive voice/web response system (IXRS) stratified by:

- Geographical region (Region 1: Asian [Japan]; Region 2: Western [Europe and US])
- Histological subtypes (nonsquamous cell carcinoma [including mixed] and squamous cell carcinoma)

Study Duration:

Patients will receive the study drug according to the proposed treatment schedule until progressive disease (PD), occurrence of intolerable side effects, removal by the Investigator, or withdrawal of consent. A patient is considered discontinued from study treatment when either TAS-114/S-1 or S-1 alone is discontinued.

For the purpose of the final analyses, the study will be considered completed when all patients have discontinued from treatment or a minimum of 12 months from the date of the first day of treatment with TAS-114/S-1 or S-1 of the last patient enrolled or until the target number of events (deaths, n=80) is reached, whichever occurs first.

Inclusion Criteria:

A patient must meet all of the following inclusion criteria to be eligible for enrollment in this study.

1. Provision of written informed consent consistent with International Council for Harmonisation (ICH)-Good Clinical Practice (GCP) guidelines and respective local law;
2. Age \geq 18 years old (\geq 20 years old in Japan);
3. Histologically diagnosed or cytologically proven advanced or metastatic NSCLC patients, either Stage IIIB/Stage IV disease (according to Version 7 of the International Association for the Study of Lung Cancer Staging Manual in Thoracic Oncology), or recurrent disease following radiation therapy or surgical resection;

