10.4.3. Survival Follow-up

All patients will be followed for survival status (alive/dead) from the time of randomization and investigator will record time of disease progression. Obtain survival status (alive/dead) at scheduled 8-week intervals until death. Survival status should be collected for up to approximately 12 months after the first dose of treatment with TAS 114/S 1 of the last patient enrolled or until the target number of events is reached, whichever occurs first, even if consent for study participation has been withdrawn. The investigator should make every effort to contact the patient or primary caregiver to determine his/her survival status. Times and dates of contact must be documented in the patient's records.

All patients will be followed for survival status (alive/dead) even if consent for other study procedures is withdrawn.

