**Table 3 – Censoring Rules for Progression-Free Survival**

Situation	End Date	Censored
Documented radiological PD	Date of the first tumor assessment that determined PD	No
Death during the study before PD	Date of death	No
Treatment discontinuation for other than radiologic PD or death with no post-baseline tumor assessments	Date of randomization	Yes
Treatment discontinuation for other than radiologic PD or death with post-baseline tumor assessments	Date of last adequate tumor assessment prior to initiation of non-study anti-cancer treatment	Yes
Patients still followed without radiologic PD as of cut-off date	Date of last adequate tumor assessment prior to cut-off date	Yes
Non-study anti-cancer treatment initiated before radiologic PD	Date of last adequate tumor assessment prior to initiation of non-study anti-cancer treatment	Yes
Death or radiologic PD after a missed (or not available/not evaluable) tumor assessment	
Date of last adequate tumor assessment prior to missed tumor assessment
 
A response assessment is considered “missed” if more than 13 weeks (91 days) has elapsed since the last image-based response assessment. If a patient develops progressive disease or dies after this interval, the tumor response assessment will be excluded from the analysis and censored at the last evaluable assessment. However, if a response assigned as CR, PR, or SD is obtained after more than 13 weeks, then the tumor response assessment will not be excluded from the analysis as long as no other censoring events have occurred.
 
Note: If patient dies within the 13 weeks from the last non-PD tumor assessment, death will be counted as a PFS event
	Yes

	unless the non-study anti-cancer treatment is initiated.	
Only non-evaluable (NE) tumor assessments after CR, PR, or SD	Date of last adequate tumor assessment prior to NE tumor assessments	Yes
No baseline tumor assessment	Date of randomization	Yes

General Considerations:
 
Tumor response assessment dates will be assigned based on the date the image was performed, not the date the image was assessed.
		

**Note:** Tumor response assessments will be considered “adequate” for analysis if they are assigned as CR, PR, SD, or PD and are not censored (e.g., obtained within 13 weeks since the last assessment and prior to initiation of non-study anti-cancer treatment: systemic anti-cancer therapy, radiotherapy or cancer surgery).

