## 6.2.2 Secondary Efficacy Variables

### 6.2.2.1 Overall Survival

Overall survival (OS) in months is defined as the time from the day of randomization to death from any cause:  $(\text{date of death} - \text{date of randomization} + 1) / 30.4375$ . Patients who were alive at the end of study will be censored at the last date the patient is known to be alive. Patients without post-baseline information will be censored at the time of randomization.

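### The SAP's follow-up end date is not the OS censoring date and has no data cut-off, so the reverse Kaplan-Meier median can overstate how long survival was observed

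*SAP*

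**What the plan says.** SAP 7.1.2 (Duration of Follow-Up) defines the period for the ITT population, by arm, as starting at randomization and running "until the last day of contact, or the day of withdrawal from study or the day of death, whichever occurs last". It then says that "follow-up will be analyzed using the reversed Kaplan-Meier method, where deaths will be censored on the date of death".

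SAP 6.2.2.1 (Overall Survival) also starts at randomization but uses a different end date: "Patients who were alive at the end of study will be censored at the last date the patient is known to be alive". The withdrawal date plays no part there.

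Neither section names a data cut-off. The PFS rules do: the entry in SAP Table 3 for patients still followed without progression is "Date of last adequate tumor assessment prior to cut-off date". The duration-of-response rules (SAP 6.2.2.3 and Table 4) do so too.

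The protocol's Survival Follow-up section (10.4.3) bears on how the two dates can separate. It says "Obtain survival status (alive/dead) at scheduled 8-week intervals until death" and "All patients will be followed for survival status (alive/dead) even if consent for other study procedures is withdrawn".

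**The concern.** Median follow-up by reverse Kaplan-Meier is the figure readers normally use to judge how mature and complete a survival curve is. It serves that purpose only if it is computed on the same times as the curve.

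Here the end dates differ for patients not known to have died. These patients supply the events in a reverse Kaplan-Meier analysis, because deaths are censored. Suppose a patient is last known alive in one month and a withdrawal date is entered several months later. OS stops at the first date and follow-up at the second. Time in which no death could have been recorded is then reported as follow-up. With no cut-off, a contact or withdrawal dated after the analysis cut-off could also count.

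**Working it through.** **No stated figure to reproduce.** The documents give no planned or expected median follow-up, no rate of loss to survival follow-up, and no rule for dating a withdrawal. The 10% loss in SAP 3.5 is loss to tumor follow-up. Every magnitude below is therefore conditional.

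**Step 1: one patient.** Let A be the last date known alive, taken as the last contact, W the withdrawal date and D the date of death.

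- Known death: both analyses end at D, so they agree.
- Not known dead: OS ends at A and SAP follow-up ends at max(A, W).
  - If W is on or before A, follow-up ends at A and the withdrawal clause does nothing.
  - If W is after A, follow-up ends at W and W - A is added. Nobody observed the patient in that interval.

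The withdrawal clause therefore either has no effect or adds unobserved time. For an individual it never shortens follow-up.

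**Step 2: why the median behaves differently.** The reverse Kaplan-Meier curve is the product of (1 - 1/n) over follow-up endings, where n is the number at risk. Move one lost patient's ending later, past some deaths and no other endings. Its factor changes from (1 - 1/n) to (1 - 1/m) with m < n, which is a bigger drop. After the new date the curve is slightly lower. If the new date still lies before the median, the median can fall. It clearly rises when the moved endings cross it.

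**Step 3: size with a median OS of 8 months.** Assumptions: 124 patients and 10 months' accrual (SAP 3.5), uniform entry, and losses spread uniformly over time. The 8 months is the lower end of the range of 8 to 10 in Protocol 6.1.

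Withdrawal dated at the cut-off, with the cut-off 3 months after last entry:

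| Lost | OS end date | SAP rule | Difference (months) |
|---|---|---|---|
| 10% | 7.57 | 7.95 | 7.95 - 7.57 = +0.38 |
| 20% | 7.14 | 7.92 | 7.92 - 7.14 = +0.78 (0.78/7.14 = 11%) |

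With the cut-off 12 months after last entry, the same model gives about +0.4 and +0.9. With no losses the two rules agree.

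Withdrawal dated 2 to 6 months after last contact, but not beyond the cut-off, changes the median by +0.03 to +0.5 months (3-month cut-off) or about -0.1 to 0 (12-month cut-off). The median falls in up to 46% of simulated trials.

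**Step 4: a second model.** Exponential survival and exponential loss, with a median OS of 7.3 months (Protocol Synopsis) and the cut-off at 80 deaths. The shortest lag is one survival contact interval: 8 weeks = 56/30.4375 = 1.84 months.

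| Lost | Withdrawal dated | OS end date | SAP rule | Mean change (months) |
|---|---|---|---|---|
| 10% | 1.84 months after last contact | 10.68 | 10.70 | +0.02 |
| 10% | 6 months after last contact | 10.60 | 10.73 | +0.13 |
| 10% | at study close | 10.60 | 11.18 | +0.58 |
| 10% | 3 months after close | 10.61 | 11.65 | +1.03 |
| 20% | 6 months after last contact | 9.91 | 10.29 | +0.38 |
| 20% | at study close | 9.90 | 11.19 | +1.30 |
| 20% | 3 months after close | 9.92 | 12.16 | +2.24 |

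(Changes were averaged before rounding.)

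Across 5% to 20% lost, median OS of 7.3 or 9.0 months, and cut-off at 80 deaths or at 12 months, the changes are:

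- lags of 1.84 to 6 months: -0.12 to +0.38 months, with mean changes below about 0.1 within or close to simulation noise;
- dated at study close: +0.25 to +2.07 months;
- dated 3 months after close: +0.48 to +3.59 months.

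The two models spread losses over time differently, hence the different upper ends. They agree that the dating of the withdrawal governs the result.

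**The case against.** **The protocol keeps following survival after consent is withdrawn.** This is the strongest defence. For such a patient the last contact can fall after the withdrawal, and taking the later date correctly keeps it. That is true, but the last-contact term alone achieves it. Where contact continues, the withdrawal clause does nothing. Where contact has stopped, it adds unobserved time.

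**The mechanism is assumed.** The documents do not say how a withdrawal date is set for a lost patient, nor call it administrative. This stands, and it is why the conclusion is that the median can overstate follow-up.

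**OS has no cut-off either.** This also stands. The contrast is with PFS and duration of response; contacts after a cut-off would extend the OS time as well as the follow-up time. The end of study mentioned in SAP 6.2.2.1 does not supply the date. The Protocol Synopsis has the study complete when all patients are off treatment, after 12 months, or "until the target number of events (deaths, n=80) is reached, whichever occurs first", while Protocol 8.1.1 lists the same triggers and takes the last to occur. Those passages must be reconciled.

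**Stronger readings that a reader might infer.**

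- That the reported median can only be too long. This holds for each patient's time but not for the median, as Steps 2 to 4 show.
- That the rule hides a difference between arms in completeness. No between-arm calculation supports this. Follow-up is reported by arm, and SAP 7.2 already summarizes follow-up status.

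**Conclusion.** The point holds as a minor one. The follow-up end date in SAP 7.1.2 does not match the OS censoring date in 6.2.2.1, and neither section names a data cut-off. For a patient lost to contact with a later withdrawal date, unobserved time counts as follow-up.

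Assuming 10% to 20% lost and a median OS of 8 months, the median is overstated by about 0.4 to 0.9 months if withdrawal is dated at the cut-off, and by more if dated after it. With lags of 2 to 6 months the change is about -0.1 to +0.5 months. The loss rate and the dating of withdrawals are assumptions, and a heavier loss pattern gives the larger values in Step 4.

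The consequence is confined to one descriptive table by arm. No test, hazard ratio, event trigger or sample size depends on it, and the SAP does not say that it will be used to judge OS maturity.

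**What to change.** In SAP 7.1.2, define follow-up as the OS time: randomization to death or last date known alive. Run the reverse Kaplan-Meier analysis by arm with the OS event indicator reversed, and delete the withdrawal clause. State one common data cut-off in both 6.2.2.1 and 7.1.2, so that both times are truncated at the same date.

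The cost is a short edit to two SAP sections. The OS variable already exists apart from the truncation, and no new data are needed. The downside is that the reported median follow-up may be slightly shorter. The change is sound whichever way the median would have moved, because the summary would then describe the times behind the OS curve.
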